### ***6.3.4 Exploratory Subgroup Assessment of Response***

Subgroup assessments of response based on patient and disease characteristics will be performed on an ad hoc basis. Reviews of the data will include evaluations of potential prognostic and predictive disease characteristics with specific interest in how these prognostic factors impact the EASI score. If a potential prognostic factor merits further consideration the exploratory analyses will at least include an NRI logistic regression analysis of the EASI-50 after 16 weeks where treatment, country and the potential factor are included in the model.

## **7 Safety Analyses**

All analyses of safety including the extent of exposure to study medication will be performed using the safety population. Reports will be generated using the overall population, and some reports will be repeated using only patients enrolled in Japan.

### 7.1.2 Treatment Compliance

Treatment compliance with the randomly assigned study medication will be evaluated at every clinic visit, so that the clinical site can reinforced the importance of treatment compliance with the patient. A patient will be considered significantly noncompliant if he or she misses more than 20% of the prescribed doses during the study, i.e. compliance < 80%. Similarly, a patient will be considered significantly noncompliant if he or she is judged by the investigator to have intentionally or repeatedly taken more than the prescribed amount of medication, i.e. compliance  $\geq$  120%. Persistent non-compliance can result in the patient being discontinued from the study.

For the purpose of analysis only the overall treatment compliance will be summarized. Treatment compliance will be derived as

$$\text{Treatment Compliance} = \frac{\text{total number of tablets dispensed} - \text{total number of tablets returned}}{\text{total number of tablets expected}}$$

The total number of tablets expected will be equal to the number of days between the date of first dose of randomly assigned study treatment and the date of the patient's last treatment period visit.

Treatment compliance will be descriptively summarized for each treatment arm. In addition, the number and percentage of patients whose compliance < 80% or  $\geq$  120% will also be presented

for each treatment arm. Treatment compliance summaries will be produced using the ITT population.

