## 2.3 Handling of Dropouts and Missing Data

Analysis of the primary response endpoint, EASI-50, will include all randomized patients and utilize a non-responder imputation (NRI) analysis. All patients who discontinue study treatment at any time prior to the time point of interest, or discontinue from the study for any reason, will be defined as non-responders for the NRI analysis. Randomized patients without at least 1 post-baseline observation will also be defined as non-responders for the NRI analysis. Secondary and exploratory efficacy responder analyses will also utilize NRI analyses and all randomized patients.

For the secondary and exploratory efficacy endpoints and clinical laboratory endpoints that are collected longitudinally, a last observation analysis will be performed by carrying forward the last post-baseline assessment. These last observation carried forward (LOCF) analyses guarantee the maximum number of randomized patients who were assessed post-baseline, will be included in the analyses. In addition, for many of the efficacy endpoints, mixed effect model repeated measures (MMRM) analyses will be performed to mitigate the impact of missing data, which will be assumed to be missing at random during the study.

If only a missing or partial date for AEs or concomitant medications is available and a complete date is required for calculations, the following algorithms will be applied:

- For the start date:
  - If year, month, and day are missing then use the minimum of the patient's first visit date or the consent date.
  - If either only month or month and day are missing then use January 1.
  - If only day is missing, impute the first day of the month.
- For the end date:
  - If year, month, and day are missing then use the patient's last visit date.
  - If either only month or month and day are missing then use December 31.
  - If only day is missing then use the last day of the month.
  - Do not expand the record past the patient's last visit.

The original missing or partial date, the imputed complete date, and the indicator variable that indicates which dates were imputed will be retained in the database.

Analyses of the safety endpoints, many of which are incidence based, will include all patients in the safety population, unless specifically stated otherwise.

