## **8 Pharmacokinetic Analyses**

Venous blood samples (approximately 5 mL per sample) for the measurement of baricitinib concentrations will be drawn at baseline (pre-dose and at 15-30 minutes post-dose) and Weeks 4 (1.5-4 hours post-dose), 8 (4-8 hours post-dose), 12 (pre-dose), and 16 (30-90 minutes post-dose) post-randomization, plus at the early termination visit, if applicable. Plasma samples from patients on active treatment will be assayed for baricitinib using liquid chromatography and tandem mass spectrometry (LC/MS/MS).

Baricitinib concentrations will be summarized by treatment and time window using summary statistics (n, mean, standard deviation, coefficient of variation [CV], minimum, median, maximum, geometric mean, and geometric CV).

A population PK analysis will be performed separately and reported in a population PK report. Exposure-response relationships between the primary and select secondary efficacy endpoints and plasma exposure may also be explored.

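### The compliance formula in SAP 7.1.2 does not measure prescribed doses: drug withdrawn well before the last treatment period visit can read as below 80%, and unreturned tablets can read as 120% or more

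*SAP*

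**What the plan says.** SAP 7.1.2 gives two definitions of significant non-compliance. A patient is non-compliant "if he or she misses more than 20% of the prescribed doses during the study", which it equates with compliance under 80%. A patient is also non-compliant if "judged by the investigator to have intentionally or repeatedly taken more than the prescribed amount of medication", which it equates with compliance of 120% or more.

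The derived variable is a ratio. The numerator is "total number of tablets dispensed" minus the number returned. For the denominator, "The total number of tablets expected will be equal to the number of days between the date of first dose" of randomised treatment and the patient's last treatment period visit. The numbers of patients below 80% and at or above 120% are then tabulated by arm in the ITT population. No exception is made for patients taken off drug before that visit, or for tablets that never come back.

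Three other places bear on this:
- SAP 7.1.1 says that the treatment period usually ends at the earlier of the Week 16 visit and the early termination visit. Its extent-of-exposure measure runs to the last dose, not to a visit.
- SAP 2.3 names stopping drug and leaving the study separately: "All patients who discontinue study treatment at any time prior to the time point of interest, or discontinue from the study for any reason".
- SAP 7 states: "All analyses of safety including the extent of exposure to study medication will be performed using the safety population". It does not mention compliance.

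**The concern.** The definition and the formula describe different quantities. The definition counts doses that were prescribed and missed. The formula counts calendar days up to a visit, and treats each one as a day on which a tablet was due. The two agree only when drug is prescribed up to that visit. If drug is withdrawn earlier, the remaining days count as missed doses although none was due.

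The numerator has its own problem. A tablet that is not returned counts as taken. When a patient disappears after a visit, the tablets handed out at that visit enter the numerator, but the denominator stops at that same visit. The result can pass 120% with no over-use and no investigator judgement, although that judgement is how the section describes the category.

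At stake is the reading of one table. Both errors follow discontinuation and unreturned supplies. If those differ between placebo, 2 mg and 4 mg, the flagged percentages will differ too, even where patients took what they were prescribed.

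**Working it through.** The SAP gives no worked compliance figure, so there is nothing to reproduce. The check applies the SAP's formula to simple cases.

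**Inputs and assumptions.** The cut-offs of 80% and 120% and the formula come from SAP 7.1.2. One tablet per day is assumed, as the formula implies. First dose is on Day 1. The wording on days can be read as v − 1 or as v for a visit on Day v, so both are shown where they differ. Visits at Weeks 1, 4, 8, 12 and 16 come from SAP 6.1. The SAP gives neither dispensing quantities nor the timing of early termination visits.

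**Case A: fully adherent, drug withdrawn on Day s, leftovers returned, last treatment period visit on Day v.**

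Compliance = s/(v − 1). This is below 0.80 when v − 1 > 1.25s, that is, when the gap v − s > 0.25s + 1. With inclusive counting the condition is v − s > 0.25s.

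- Stop Day 28, visit Day 37: 28/36 = 77.8% (inclusive 28/37 = 75.7%). Flagged.
- Stop Day 28, gap 7 days: 28/34 = 82.4% (inclusive 28/35 = 80.0%). Not flagged.
- Stop Day 28, gap 14 days: 28/41 = 68.3% (inclusive 28/42 = 66.7%). Flagged.
- Visit 0 to 1 day after the last dose, stops from Day 14 on: 93% to 108%. Not flagged.

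| Stop day | Smallest gap that flags (inclusive to exclusive count) | Compliance if kept off drug to Week 16 (112 days) |
|---|---|---|
| 14 | 4–5 days | 14/112 = 12.5% |
| 28 | 8–9 days | 28/112 = 25% |
| 56 | 15–16 days | 56/112 = 50% |
| 84 | 22–23 days | 84/112 = 75% |

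For a patient kept to Week 16, any stop up to Day 89 is flagged (89/112 = 79.5%); Day 90 is not (90/112 = 80.4%).

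**Case B: fully adherent to the last attended visit, then lost, with the supply given at that visit unreturned.** Supply is assumed to last to the next scheduled visit.

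Compliance = (days to visit + unreturned tablets)/(days to visit). It reaches 120% when unreturned tablets ≥ 0.2 × days to visit.

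| Last visit | Compliance | Unreturned tablets needed for 120% |
|---|---|---|
| Week 1 | (7 + 21)/7 = 400% | 2 (0.2 × 7 = 1.4) |
| Week 4 | (28 + 28)/28 = 200% | 6 (0.2 × 28 = 5.6) |
| Week 8 | (56 + 28)/56 = 150% | 12 (0.2 × 56 = 11.2) |
| Week 12 | (84 + 28)/84 = 133% | 17 (0.2 × 84 = 16.8) |

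The percentages rest on the assumed supply. The last column does not.

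**Day count.** SAP 8 schedules the Week 16 sample after a dose ("16 (30-90 minutes post-dose) post-randomization"), so the visit day can be a dosing day. With exclusive counting, a perfect taker then scores (k + 1)/k, where k is the days between. That is 113/112 = 100.9% at Week 16, and it reaches 120% only for k ≤ 5, a termination visit by Day 6.

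**After the fix below.** Case A becomes 28/28 = 100% whatever the gap. In Case B the interval opened at the last visit drops out, leaving 28/28 = 100% for the Week 4 example. A patient who quits on their own on Day 28 while drug is prescribed to Day 56 scores 28/56 = 50% and is still flagged.

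**The case against.** The strongest objection is that the SAP's denominator usually stops at the early termination visit. If that visit follows promptly on the last dose, compliance is about 100% and nothing is misreported. This stands. A reader might infer that adherent early stoppers are flagged as a rule. They are flagged only when the gap exceeds roughly a quarter of the days dosed. The 25% figure needs a patient who stays in the treatment period off drug to Week 16. SAP 2.3 separates stopping drug from leaving the study in order to define non-responders; it does not say that such patients keep attending.

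A reader might also take the drop-out ceiling in SAP 1.3 (20% of 120, or 24 patients) as the number misclassified. It is not. Neither the gaps nor the number lost with tablets in hand is known.

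Nor do the documents support a claim that the efficacy results are distorted. Compliance defines no analysis population and enters no test. Discontinuation reasons, adverse events leading to drug discontinuation, and exposure are each tabulated by arm, so a careful reader can partly separate withdrawal from poor adherence.

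Three lesser points carry little weight. The day-count ambiguity matters only for very early terminations. Tablets per day may be given in the protocol. Using ITT for compliance is an explicit choice; it only leaves never-dosed patients without a value, which the SAP should say.

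What the objection does not remove is the mismatch inside 7.1.2. The section defines the flags one way and computes them another, with no rule for withdrawn drug or unreturned tablets.

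**Conclusion.** The point holds in a limited form. Followed exactly, the derivation can flag adherent patients below 80% when drug is withdrawn well before the last treatment period visit, and can flag patients lost with unreturned tablets at 120% or more. Both results contradict the section's own definitions. The examples assume one tablet per day, and those for lost patients also assume a supply lasting to the next visit.

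How often this happens, and whether it differs by arm, cannot be computed from the SAP. The effect is confined to the descriptive compliance table. Severity is minor: worth correcting because it is cheap, but no threat to the primary comparison.

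**What to change.** Change the derivation in SAP 7.1.2 as follows, keeping the 80% and 120% cut-offs.

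- **Denominator.** Set tablets expected to the number prescribed from first dose through the last day study drug was prescribed. That day is the earlier of the recorded decision to discontinue treatment and the last treatment period visit. Count both end days. Do not end it at the last dose taken: a patient who stops on their own on Day 28 while still prescribed drug would then score 28/28 = 100%, which would hide real non-compliance.
- **Unreturned supply.** Leave any dispensing interval with no return count out of both numerator and denominator. Set compliance to missing if no interval remains. The new denominator alone does not cure the 120% problem, because the numerator would still count unreturned tablets as taken.
- **Never-dosed patients.** State that they have no compliance value, or summarise in the Safety population.

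The cost is a few sentences and one reprogrammed variable. The downside is that a few patients will have missing compliance; report their number by arm beside the table.

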## 7.2 Adverse Events

AEs will be collected from the day the patient gives informed consent until 30 days after the final dose of study drug or until resolution of all serious adverse events (SAEs). Only those AEs that emerge or worsen after the date of first dose of randomly assigned study medication, i.e. treatment emergent adverse events (TEAE), will be reported. Adverse events with a missing start date will also be classified as TEAE.

Summaries of TEAE will include the number of patients with at least one TEAE for each treatment arm. When reporting by system organ class (SOC) and preferred term (PT), the reports will present the SOC in alphabetical order; while PTs within the SOC will be presented in order of overall decreasing frequency of occurrence in the combined baricitinib arms. A patient with multiple TEAEs (different PTs) coded to the same SOC will be counted only once for that SOC, but will be counted each time for different PTs within that SOC. A patient with separate events of the same PT (different start/stop dates) will be counted only once in the frequency tables for that PT.

TEAEs will be reported using the treatment that the patient received.

No statistical testing will be performed for comparisons of TEAEs.

An overview of all TEAEs will also be provided by treatment group using the types of AEs defined in the following subsections.

### 7.2.1 Treatment-Emergent Adverse Events

TEAEs will be summarized by SOC and PT for each treatment arm. In addition, a presentation of TEAE preferred terms in decreasing frequency in the combined baricitinib treatment arms will be provided.

### 7.2.2 Treatment Related TEAE

Every AE will be assessed by the investigator for its relationship to the randomly assigned study medication. The subset of TEAE considered by the investigator as related to study treatment will be called treatment related TEAE.

Treatment related TEAE will be summarized for each treatment arm by SOC and PT and by decreasing frequency in the combined baricitinib arms.

### 7.2.3 Serious Treatment-Emergent Adverse Events

An SAE is an AE that met one or more of the following criteria:

- death
- initial or prolonged inpatient hospitalization
- a life-threatening experience (that is, immediate risk of dying)

- persistent or significant disability/incapacity
- congenital anomaly/birth defect or
- considered significant by the investigator for any other reason

Serious TEAEs will be summarized for each treatment arm by SOC and. A listing of all SAE will also be provided. The listing will be sorted by treatment arm, country, patient ID and study day of onset.

#### ***7.2.4 TEAE Resulting in Death***

If there are any TEAE that result in death, then a listing of all deaths will be provided. The listing will be sorted by treatment arm, country, patient ID and study day of onset.

#### ***7.2.5 TEAE Leading to Study Drug Discontinuation***

For every AE in the eCRF the investigator indicates whether the action taken with respect to the study medication was dose not changed or drug withdrawn.

The TEAE that lead to study drug discontinuation will be summarized for each treatment arm by SOC and PT and by decreasing frequency in the combined baricitinib. A listing of the TEAE that lead to study drug discontinuation will also be provided.

#### ***7.2.6 TEAE by Maximal Severity***

Every AE will be graded by the investigator as mild, moderate, or severe, so for each patient the greatest severity observed can be obtained by comparing the severity of all of a patient's TEAE that share the same SOC or PT. A table of TEAE by maximal severity will be prepared for each treatment arm by SOC and PT.

#### ***7.2.7 Adverse Events of Special Interest***

Adverse events or laboratory results of special interest include infections; myelosuppressive events of anaemia (haemoglobin decreased), leukopenia (white blood cell count decreased), neutropenia (neutrophil count decreased), lymphopenia (lymphocyte count decreased), thrombocytopenia (red blood cell count decreased), thrombocythaemia (platelet count increased); hyperlipidaemia (lipids increased); hypercholesterolemia (cholesterol increased); and elevations in hypertransaminasaemia (aminotransferase increased) and hyperbilirubinemia (bilirubin increased). All TEAE for which the PT contains any of the above terms or that belong to the SOC 'Infections and infestations' will be considered an AE of special interest. The TEAE of special interest will be summarized for each treatment arm by SOC and PT and by decreasing frequency in the combined baricitinib arms.

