### **7.3 Clinical Laboratory Results**

Blood samples for hematology and serum chemistry and urine samples for urinalysis will be collected at baseline and Weeks 4, 8, 12, and 16 post-randomization. Blood samples for fasting lipid profiles will be collected at baseline and Week 16 post-randomization, and blood samples for immunoglobulins will be collected at baseline and Weeks 8 and 16 post-randomization. If a

patient decides to discontinue early from the study, samples for each of the parameters will be collected prior to discontinuation.

Analyses of laboratory values will be produced using the measurements collected the scheduled time points. The unscheduled assessments will only appear in data listings. An exception will be made for the analyses of the last measured values which for patients who do not have a measurement at Week 16 will be derived using the last collected scheduled or unscheduled measurement.

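### The term list that selects adverse events of special interest pairs thrombocytopenia with a red-cell measure, so a laboratory-style platelet-decrease term would not be selected (minor)

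*SAP*

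**What the plan says.** SAP section 7.2.7 names infections and ten conditions as being of special interest. Each of the ten conditions is followed in brackets by a laboratory change. The two platelet-related entries read "thrombocytopenia (red blood cell count decreased), thrombocythaemia (platelet count increased".

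The list is then made operative. An event is of special interest if it belongs to the infections class or meets this rule: "All TEAE for which the PT contains any of the above terms". The output is defined next: "The TEAE of special interest will be summarized for each treatment arm by SOC and PT", together with a presentation by decreasing frequency in the combined baricitinib arms.

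Section 7.2 adds a further display: "An overview of all TEAEs will also be provided by treatment group using the types of AEs defined in the following subsections". Special-interest events are one of those types. The same section states: "No statistical testing will be performed for comparisons of TEAEs".

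**The concern.** A wrong word in background text would be cosmetic. Here the words are the selection criteria that a programmer will implement. The thrombocytopenia entry points to red cells, although the very next entry shows that the platelet count is the measure for the opposite condition. No other section of the SAP corrects it.

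At stake is whether the special-interest displays capture reported platelet falls, which the SAP names among the myelosuppressive events. As written, the list has a laboratory-style term for a platelet rise but none for a platelet fall.

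**Working it through.** The SAP states no figure to reproduce here. The check is to apply its rule literally.

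**Step 1. The list (7.2.7).** There are 10 condition–measure pairs, 6 of them in the myelosuppressive group:

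| Condition | Bracketed measure | Own measure? |
|---|---|---|
| anaemia | haemoglobin, decreased | yes |
| leukopenia | white cells, decreased | yes |
| neutropenia | neutrophils, decreased | yes |
| lymphopenia | lymphocytes, decreased | yes |
| thrombocytopenia | red cells, decreased | **no** |
| thrombocythaemia | platelets, increased | yes |

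The other four pairs (lipids, cholesterol, aminotransferase, bilirubin) each match their condition. So 1 of 10 pairs is out of pattern, which is 1 of the 6 myelosuppressive pairs. Of the 5 decrease-type conditions, 4 carry their own measure.

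**Step 2. The rule.** Select an event if its preferred term contains any listed string, ignoring case. *Above terms* can be read in two ways: condition names plus bracketed wordings (20 strings), or condition names only (10 strings). The preferred-term wordings tested are assumptions. *Platelet count decreased* mirrors the SAP's own bracketed wording for the platelet rise.

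| Preferred term (assumed) | As written, 20 strings | Condition names only | After correcting one string (20 strings) |
|---|---|---|---|
| Thrombocytopenia | selected | selected | selected |
| Platelet count decreased | **not selected** | **not selected** | selected |
| Red blood cell count decreased | selected | not selected | not selected |
| Platelet count increased | selected | not selected | selected |
| Haemoglobin decreased | selected | not selected | selected |

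The omission holds on both readings. The red-cell inclusion holds only if the bracketed wordings count. That is the more natural reading: on the other one, the bracketed wordings tested here would select nothing.

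**Step 3. Displays that use the selection.** Section 7.2.7 gives 2 (by class and term; by decreasing frequency) and the overview in 7.2 gives 1: 2 + 1 = 3.

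**Step 4. Where a missed event would still appear.**
- Section 7.2.1: "TEAEs will be summarized by SOC and PT for each treatment arm", plus a listing of terms by frequency.
- Section 7.2.6: "A table of TEAE by maximal severity will be prepared for each treatment arm by SOC and PT".
- Section 7.3.1: value and changes by arm and visit for every quantitative laboratory parameter, whatever the event coding.
- Section 7.3.2: low/normal/high shift tables for each parameter, from baseline to Week 16 and to the last observation.

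The last two cover platelets on the assumption that the platelet count is part of the haematology panel, which the SAP does not itemise.

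**The case against.** The strongest reply is that this is an obvious slip with almost no consequence. The next entry shows what was meant, and an experienced programmer would probably query it. Platelet values are summarised by visit and in shift tables without reference to event coding. No event is lost from the trial report, nothing is tested, and the omission rests on an assumed term wording.

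Most of this stands, and it is why the point is minor. Two qualifications remain. The validation in SAP section 2 checks outputs for consistency with the plan, so a second programmer following the same list could reproduce the same omission. The laboratory summaries are also not a full substitute for the special-interest table. The planned shift tables compare baseline only with Week 16 and the last observation, with other time points added only if data review warrants it. A platelet fall that recovered in between would show in the by-visit statistics, for instance as a minimum, and not as a count of patients.

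Three stronger readings are tempting and are not supported.

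- A reader might infer that selecting a red-cell decrease is certainly an error. The SAP does not show this. The group is introduced as myelosuppressive events, and a red-cell decrease could be a wanted term in the wrong place. The selection also depends on the bracketed wordings counting as terms.
- A reader might infer that platelet falls would go unreported. Step 4 of the working shows otherwise.
- A reader who goes on to section 7.3 might see a related defect in the liver threshold counts of 7.3.2, which speak of any post-baseline elevation, because 7.3 says "Analyses of laboratory values will be produced using the measurements collected the scheduled time points". That is no contradiction. Section 7.3 sets an explicit scheduled-only rule with one named exception, and any elevation among the analysed values is compatible with it. Adding unscheduled draws would be a trade-off, because patients with more repeat draws have more chances of an abnormal value.

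**Conclusion.** The point holds, as a minor one. The thrombocytopenia entry in 7.2.7 is mispaired, and because the list is the selection rule, the mispairing changes which events are selected. A laboratory-style platelet-decrease term is missed on either reading of the rule. A red-cell decrease enters through the thrombocytopenia entry if the bracketed wordings count.

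The size is 1 wrong string among 10 pairs, affecting 3 descriptive displays. The SAP gives no basis for estimating how many events this touches. It is zero if every platelet fall is coded *thrombocytopenia* and no red-cell decrease is reported. Primary and secondary efficacy results are untouched.

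The conclusion assumes that the rule is implemented literally and that a preferred term worded like *platelet count decreased* can occur. The SAP names the coding dictionary (section 2.6) but lists no preferred terms.

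**What to change.** In SAP section 7.2.7, change the entry to thrombocytopenia (platelet count decreased). Check this string, and preferably the rest of the list, against the actual preferred terms. Section 2.6 reports with the dictionary version current at database lock, so confirm the match against that version.

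Decide whether a red-cell decrease is also of special interest. If it is, list it separately with anaemia, because the corrected entry no longer selects it.

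The cost is one corrected term, one short check and, if wanted, one added term. No new data or tables are needed. Making the change before the displays are programmed avoids deciding after unblinding which events qualify.

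### The special-interest adverse event search matches literal text in the preferred term, but its list mixes British and American spelling, so some events coded to a named diagnosis will be missed

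*SAP*

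**What the plan says.** SAP Section 7.2.7 names the conditions of special interest and then gives the rule that picks the events: "All TEAE for which the PT contains any of the above terms", or, as the alternative, membership of the infections system organ class. So there are two ways in: the preferred term contains a listed term, or the event falls in the infections class. For the haematology, lipid and liver conditions only the first applies.

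Apart from infections, ten conditions are named, each followed by a laboratory-style term in brackets. The spelling changes within the list:

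- British: "myelosuppressive events of anaemia (haemoglobin decreased" and "thrombocythaemia (platelet count increased); hyperlipidaemia (lipids increased".
- American: "hypercholesterolemia (cholesterol increased".
- Both in one phrase: "elevations in hypertransaminasaemia (aminotransferase increased) and hyperbilirubinemia (bilirubin increased".

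Section 2.6 says that adverse events are coded in MedDRA, using the newest release available when the database is locked. It states no spelling convention. The SAP gives no list of preferred terms, no codes and no standardised query for these conditions.

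**The concern.** A containment rule works only if the listed string appears letter for letter inside the coded term. A list with both *-aemia* and *-emia* endings cannot fit a dictionary that uses one of them throughout. Whichever spelling the dictionary has, some listed diagnoses fail to match.

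The consequence is uneven. An event coded to the diagnosis can drop out of the special-interest tables, while the same finding coded as a laboratory change stays in. The count for a condition that the sponsor singled out then depends partly on how the event was worded and coded. A reader of the table cannot see which events were left out.

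**Working it through.** The plan gives no figure to reproduce. The check is a substring test on the terms as printed.

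**Inputs.** The ten diagnoses and ten bracketed laboratory terms come from Section 7.2.7. The one assumption is that the dictionary spells its preferred terms consistently. The SAP does not say which way, so both cases are shown.

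**Method.** Rewrite each term in consistent British and then consistent American spelling, and ask whether the result contains any listed term exactly as printed.

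**Split of the ten diagnoses.**

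- British as printed: anaemia, thrombocythaemia, hyperlipidaemia, hypertransaminasaemia (4).
- American as printed: hypercholesterolemia, hyperbilirubinemia (2).
- Treated as the same in both: leukopenia, neutropenia, lymphopenia, thrombocytopenia (4).
- Total: 4 + 2 + 4 = 10.

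**Results for the six spelling-sensitive conditions.**

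| Condition as printed | Diagnosis found, British | Diagnosis found, American | Bracketed term found, British | Bracketed term found, American |
|---|---|---|---|---|
| anaemia | yes | no | yes | no |
| thrombocythaemia | yes | no | yes | yes |
| hyperlipidaemia | yes | no | yes | yes |
| hypertransaminasaemia | yes | no | yes | yes |
| hypercholesterolemia | no | yes | yes | yes |
| hyperbilirubinemia | no | yes | yes | yes |

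The other four conditions match by both routes under either spelling.

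**Counts.**

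- British dictionary: 10 − 2 = 8 diagnoses match, and all 10 bracketed terms match. No condition loses both routes.
- American dictionary: 10 − 4 = 6 diagnoses match, and 10 − 1 = 9 bracketed terms match, because *hemoglobin* does not contain *haemoglobin*. One condition, anaemia, loses both routes.
- If each term is listed in both spellings, all 10 diagnoses and all 10 bracketed terms match under either convention, so none is missed.

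The 2 of 10 and the 4 of 10 are alternatives, since only one spelling will apply. They must not be added.

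**Scale of one event.** Section 1.3 plans about 120 patients at 4:3:3, so each baricitinib arm has about 120 × 3/10 = 36, and one patient is 1/36 = 2.8 percentage points. That is the weight of any single patient in any table for that arm. It is not an estimate of how many would be missed.

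**The case against.** The strongest reply is that the rule is prose, not program code. A sensible programmer would search for each condition in the dictionary's own spelling, and Section 2 requires independent validation programming, independent review of outputs and a senior statistical review. This makes an unnoticed error less likely but does not exclude it. Two programmers who copy the printed strings will agree with each other and miss the same events. If one of them harmonises the spelling and the other does not, the SAP gives no basis for settling the difference.

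It can also be said that the dictionary's spelling, and which of the ten words are actual preferred terms, cannot be seen from the document. That is true, and it is why the sizes are conditional. The conclusion that some listed diagnosis fails does not depend on which spelling applies, only on there being one.

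Two limits on the consequence stand in full:

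- A reader might infer that the affected conditions disappear from the special-interest tables altogether. The SAP does not support that. The bracketed laboratory terms are also on the list, so events coded that way are still selected, with anaemia under American spelling as the only exception.
- A reader might infer that safety information is lost from the report. It is not. Every treatment-emergent event still appears by class and preferred term under Section 7.2.1 and by maximal severity under Section 7.2.6. Laboratory values are summarised under Sections 7.3.1 and 7.3.2, including counts of transaminase, bilirubin and alkaline phosphatase elevations. Infections enter by class and are unaffected. Section 7.2 plans no testing of these events.

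**Conclusion.** The point holds for events coded to the diagnosis term. Applied literally, the Section 7.2.7 search misses such events for 2 of the 10 named conditions under British spelling (hypercholesterolaemia, hyperbilirubinaemia) or 4 of the 10 under American spelling (anemia, thrombocythemia, hyperlipidemia, hypertransaminasemia). Only anaemia, and only under American spelling, is lost by both routes.

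This rests on two assumptions: that the dictionary uses one spelling throughout, and that the rule is programmed as written. The result would be an undercount confined to the descriptive special-interest tables. No efficacy result or hypothesis test depends on it. The 2.8 points per patient should not be read as an expected loss, because the SAP gives no event rates or coding patterns from which one could be derived.

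It is still more than a copy-editing matter: this sentence is the operative definition of the special-interest set, and no other part of the SAP corrects it.

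**What to change.** At the least, write each diagnosis and each bracketed laboratory term in the dictionary's spelling, or list both spellings. The laboratory terms are already in the rule, so for this purpose only *haemoglobin* needs attention among them.

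Preferably, replace the text match with an explicit list of preferred terms for each condition, taken from the dictionary version used for reporting and fixed before unblinding. Section 2.1 gives a small sponsor team, including the project statistician, unblinded access around the last Week 12 visit, while Section 2.6 settles the dictionary version only at lock. The list is therefore best drafted before that access, and later updated only for changes in the dictionary.

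The same revision should correct a separate error in the sentence: thrombocytopenia is glossed there with a red-cell term, so a fall in platelet count is not among the search terms under any spelling. Harmonising the spelling would not repair that.

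The cost is a short term list to prepare and check. Nothing changes in data collection or in any other analysis.
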